3.3.4 Discontinuation of patients from treatment or assessments

Patients may discontinue trial treatment or withdraw consent to trial participation as a whole ("withdrawal of consent") with very different implications; please see sections [3.3.4.1](#) and [3.3.4.2](#) below.

However, if the patients agree, they should stay in the trial. Even if continued trial treatment is not possible, they should attend further trial visit to ensure their safety.

Measures to control the withdrawal rate include careful patient selection, appropriate explanation of the trial requirements and procedures prior to trial enrolment, as well as the explanation of the consequences of withdrawal.

The decision to discontinue trial treatment or withdraw consent to trial participation and the reason must be documented in the patient files and CRF. If applicable, consider the requirements for Adverse Event collection reporting (please see section [5.2.6.2](#)).

3.3.4.1 Discontinuation of trial treatment

Ideally, the patient should attend the End of Trial visit. Should the patient not agree, at least phone contact should occur at the scheduled visit time point to collect the most relevant information: vital status (please see section [5.2.6.2.1](#)), outcome events, adverse events, or last contact date in case of lost to follow-up.

An individual patient will discontinue trial treatment if:

- The patient wants to discontinue trial treatment. The patient will be asked to explain the reasons but has the right to refuse to answer.
- The patient has repeatedly shown to be non-compliant with important trial procedures and, in the opinion of the investigator, the safety of the patient cannot be guaranteed as he / she is not willing or able to adhere to the trial requirements in the future.
- The patient needs to take concomitant medication that interferes with the safety of the investigational medicinal product or other trial treatment (refer to sections [4.2.2.1](#)).
- The patient can no longer receive trial treatment for medical reasons such as surgery, adverse events, other diseases, or pregnancy. The patient shows disease progression/worsening that precludes further participation in the trial per investigator's clinical judgement. The participant develops suicidal ideation of type 4 or 5 in the C-SSRS (i.e., active suicidal thought with intent but without specific plan, active suicidal thought with plan and intent) or suicidal behavior (i.e. actual attempt, interrupted attempt, aborted attempt or preparatory acts or behavior). If new efficacy / safety information becomes available, Boehringer Ingelheim will review the benefit-risk-assessment and, if needed, discontinue the trial treatment for all patients or take any other appropriate action to guarantee the safety of the trial patients.

Even if the trial treatment is discontinued, the patients remain in the trial and, given their agreement, will undergo the procedures for early treatment discontinuation and follow-up as outlined in the [Flow Chart](#) and section [6.2.3](#).

3.3.4.2 Withdrawal of consent to trial participation

Patients may withdraw their consent to trial participation at any time without the need to justify the decision.

If a patient wants to withdraw consent, the investigator should be involved in the discussion with the patient and explain the difference between trial treatment discontinuation and withdrawal of consent to trial participation, as well as explain the options for continued follow-up after trial treatment discontinuation, please see section [3.3.4.1](#) above.

3.3.4.3 Discontinuation of the trial by the sponsor

Boehringer Ingelheim reserves the right to discontinue the trial overall or at a particular trial site at any time for the following reasons:

- Failure to meet expected enrolment goals overall or at a particular trial site.

Proprietary confidential information © 2024 Boehringer Ingelheim International GmbH or one or more of its affiliated companies

- New efficacy or safety information invalidating the earlier positive benefit-risk-assessment, please see section [3.3.4.1](#).

Deviations from GCP, the trial protocol, or the contract impairing the appropriate conduct of the trial.

Further treatment and follow up of patients affected will occur as described in section [3.3.4.1](#). The investigator / the trial site will be reimbursed for reasonable expenses incurred in case of trial termination (except in case of the third reason).

4. TREATMENTS

4.1 INVESTIGATIONAL TREATMENTS

The trial medication will be provided by Boehringer Ingelheim or a designated CRO.

4.1.1 Identity of the Investigational Medicinal Products

Table 4.1.1:1 Test product 1

Substance:	Atomoxetine [REDACTED]®
Pharmaceutical formulation:	Capsules
Source:	[REDACTED]
Unit strength:	40 mg
Posology:	80 mg on Day 1 (after randomization); 2-0-0 40 mg QD from Day 2 to day 7 inclusive; 1-0-0 80 mg QD from Day 8 to day 14 inclusive; 2-0-0
Mode of administration:	Per os

Table 4.1.1: 2 Test Product 2

Substance:	Placebo to Atomoxetine tablets available on the market
Pharmaceutical formulation:	Film-coated tablet
Source:	BI Pharma GmbH & Co. KG, Germany
Unit strength:	NA
Posology:	2 tablets QD on Day 1 (after randomization); 2-0-0 1 tablet QD from Day 2 to day 7 inclusive; 1-0-0 2 tablets QD from Day 8 to day 14 inclusive; 2-0-0
Mode of administration:	Per os

Any unused product or waste material will be disposed of in accordance with local requirements.

4.1.2 Selection of doses in the trial and dose modifications

Atomoxetine is approved for treatment of ADHD. The doses of Atomoxetine selected for this trial generally follow the approved posology of Atomoxetine for the treatment of ADHD (initiated at a total daily dose of 40 mg for a minimum of 7 days prior to upward dose titration according to clinical response and tolerability up to 80 mg daily).

The higher first dose is necessary to investigate whether a single dose of atomoxetine reduces impulsivity in behavioral laboratory tasks and deemed clinically acceptable under close medical surveillance.

4.1.3 Method of assigning patients to treatment groups

After the assessment of all in- and exclusion criteria, each eligible patient will be randomised to a treatment group according to a randomisation plan in a 1:1 ratio at Day1/visit 3 via Interactive Response Technology (IRT). Note that the medication number is different from the patient number (the latter is generated during screening via the IRT System).

4.1.4 Drug assignment and administration of doses for each patient

The medication assignment will be provided through IRT. The assigned medication numbers must be entered in the eCRF, and the corresponding medication kits must be given to the patient. At Visit 3, after randomization, patients will receive their first medication kit.

Administration of trial medication will be performed after subjects have fasted overnight; fasting is to start no later than 10 h before the scheduled dosing.

The first dose of trial medication will be taken at the study site under supervision of the dedicated site staff. Subjects will be kept under close medical surveillance until 4 h after the first drug administration.

On days 1 and 8, patients will receive medication kits containing supplies for a total of 7 treatment days (7 treatment days plus 1 day reserve to cover for possible damage). Patients will be instructed to take the study medication orally with water and without food. Return of the used/unused medication kits will occur at Visit 3 (day 8) and Visit 4 (day 14). Patients should be instructed not to take their trial medication in the morning of visits on days 8 and 14, as patients will be dosed at the site after pre-dose PK sampling.

Table 4.1.4: 1 Dosage and treatment schedule

Treatment	Substance	Unit strength	Dosage	Total dose
T (Test)	Atomoxetine	40 mg	80 mg doses on day 1 40 mg doses on Days 2 to Day 7 (6 days) 80 mg doses on Days 8 to Day 14 (7 days)	800 mg
R (Reference)	Placebo	NA	2 tablets on day 1 1 tablet on Days 2 to Day 7 (6 days) 2 tablets on Days 8 to Day 14 (7 days)	NA

4.1.5 Blinding and procedures for unblinding

4.1.5.1 Blinding

This is a double-blind trial, therefore patients, Investigators (outcome assessors) and everyone involved in trial conduct (except the trial personnel involved in the dispensing the trial medication—third-party blinding) will remain blinded with regard to the randomized treatment assignments until after the final database lock, in order to limit the occurrence of any bias which the knowledge of treatment may have.

Taking into account that Atomoxetine and Placebo differ in their presentations, medications will be packaged to the identical blisters, and the secondary packaging (boxes containing blisters) will be identical for both Atomoxetine and Placebo, allowing the blinding of the site staff. The appearance of both presentations used in the study matches the medication available on the market, therefore the patient's blindness to the treatment will be granted. Blinding of treatments to the site will be maintained by using a third-party blinding, where the study drug will be dispensed/administered to the patients on days 1, 8 and 14 by persons who are independent of the other clinical trial procedures and not involved in other aspects of the study. Details on the medication handling at the site will be provided in the Pharmacy manual and filed in ISF.

All trial data will be handled open label. This means that trial functions of the sponsor and responsible global vendor are unblinded (including CTL/PM, data managers, statisticians, bioanalysts, pharmacokineticists, pharmacometrists).

This is acceptable because they are neither in contact with subjects nor with site staff.

Access to the randomisation schedule will be controlled and documented by a signed confidentiality statement, which will be stored in the TMF.

4.1.5.2 Unblinding and breaking the code

Emergency unblinding will be available to the investigator via IRT. It must only be used in an emergency situation when the identity of the trial drug must be known to the investigator in order to provide appropriate medical treatment or otherwise assure safety of trial participants. The reason for unblinding must be documented in the source documents and/or appropriate CRF page.

Due to the requirements to report Suspected Unexpected Serious Adverse Reactions (SUSARs), it may be necessary for a representative from BI's Pharmacovigilance group to access the randomisation code for individual patients during trial conduct. The access to the code will only be given to authorised Pharmacovigilance representatives for processing in the PV database system and not be shared further.

4.1.6 Packaging, labelling, and re-supply

The investigational medicinal products will be provided by BI or a designated CRO. They will be packaged and labelled in accordance with the principles of Good Manufacturing Practice (GMP). Re-supply to the sites will be managed via an IRT system, which will also monitor expiry dates of supplies available at the sites.

For details of packaging and the description of the label, refer to the ISF.

4.1.7 Storage conditions

Drug supplies will be kept in their original packaging and in a secure limited access storage area according to the recommended storage conditions on the medication label. A temperature log must be maintained for documentation.

If the storage conditions are found to be outside the specified range, the Clinical Research Associate CRA (as provided in the list of contacts) must be contacted immediately.

4.1.8 Drug accountability

The investigator or designee will receive the investigational drugs delivered by the sponsor or delegate when the following requirements are fulfilled:

- Approval of the clinical trial protocol by the RA / ethics committee,
- Availability of a signed and dated clinical trial contract between the sponsor or delegate and the investigational site,
- Approval / notification of the regulatory authority, e.g. competent authority,
- Availability of the curriculum vitae of the Principal Investigator,
- Availability of a signed and dated clinical trial protocol,

Investigational drugs are not allowed to be used outside the context of this protocol. They must not be forwarded to other investigators or clinics. Patients should be instructed to return unused investigational drug.

The investigator or designee must maintain records of the product's delivery to the trial site, the inventory at the site, the use by each patient, and the return to the sponsor or warehouse / drug distribution centre or alternative disposal of unused products. If applicable, IRT will track whether IMP is destroyed or returned to distribution vendor, and will maintain records of the disposal.

These records will include dates, quantities, batch / serial numbers, expiry ('use- by') dates, and the unique code numbers assigned to the investigational medicinal product and trial patients. The investigator or designee will maintain records that document adequately that the patients were provided the doses specified by the Clinical Trial Protocol (CTP) and reconcile all investigational medicinal products received from the sponsor. At the time of return to the appointed CRO / or destruction on site , the investigator or designee must verify that all unused or partially used drug supplies have been returned by the clinical trial patient and that no remaining supplies are in the investigator's possession.

4.2 OTHER TREATMENTS, EMERGENCY PROCEDURES, RESTRICTIONS

4.2.1 Other treatments and emergency procedures

There are no specific rescue drugs foreseen for the treatment of AEs. There are no special emergency procedures to be followed.

Atomoxetine is relatively non-toxic in overdose. Single-drug overdoses involving over 1500 mg of atomoxetine have not resulted in death. The recommended treatment for atomoxetine overdose includes use of activated charcoal to prevent further absorption of the drug.

In case of AEs in need of treatment, the investigator can authorize an appropriate therapy. In those cases, subjects will be treated as necessary and, if required, kept under supervision at the trial site or transferred to a hospital until all medical evaluation results have returned to an acceptable level.

The investigator must provide follow-up medical care for all patients who are prematurely withdrawn from the study or must refer them for appropriate ongoing care according to local guidelines and daily practice, respectively.

4.2.2 Restrictions

4.2.2.1 Restrictions regarding concomitant treatment

Following medications are prohibited during the treatment period:

- All psychotropic medications, concomitant use of CYP2D6 inhibitors, sympathomimetics, Monoamine Oxidase Inhibitors (MAOI) should not be taken for two weeks before, during and 2 weeks after treatment with Atomoxetine, and at least 5 half-lives before base-line visit;

Proprietary confidential information © 2024 Boehringer Ingelheim International GmbH or one or more of its affiliated companies

- Antihypertensive Drugs, Pressor Agents (e.g., dopamine, dobutamine), beta 2 agonists or other drugs that increase/decrease blood pressure should be used cautiously because of possible effects on blood pressure and heart rate;
- Use of alternative or traditional medicines (e.g. Chinese traditional medicine, herbal medication, St. John's Wort, Ayurveda medications, etc.).

Occasional (single dose) concomitant use of benzodiazepines and non-benzodiazepine hypnotics are allowed during study at a dose equivalent to ≤ 1.0 mg of lorazepam per day, for the management of AEs (e.g. anxiety and/or insomnia). Such drugs should be stopped immediately after the AE is resolved and should be avoided within approx. 48 hours before planned impulsivity testing.

Stable therapy with SSRI might be continued with caution as judged by investigator (except for Paroxetine and Fluoxetine which are inhibitors of CYP2D6). If patient receiving current treatment with SSRI, the dose must have been stable for a minimum of 2 months prior to screening and when possible maintained at a lower range.

In case of AEs, any treatment deemed necessary per the clinical judgment of investigator for the management of AEs considering patient safety is allowed.

Investigators are encouraged to adhere to the restrictions listed in the [Appendix 10.2](#) or contact the sponsor or sponsor's medical representative.

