6.2.1 Screening and run-in periods

Informed Consent for trial participation

All patients must sign an Informed Consent consistent with ICH-GCP guidelines prior to any study specific procedures. Please refer to [section 8.1](#) for details.

Screening Period

The Screening period, i.e. the phase before the first administration of the trial drug, starts at Visit 1. The Screening period may be as long as 28 days but should be kept as short as possible.

- IRT All patients who are screened must be registered with IRT. If the screening results in a screen failure, patient must be recorded as screen failure in IRT as soon as

possible and within the 28-day screening period. Details of IRT procedures can be found in the IRT Manual filed in the ISF.

- During the screening visit, demographics information will be collected. This includes: age on the day of informed consent (in years), Sex (male, female in order to describe the subject's sex at birth), and social status (years of education and employment status). For women: of childbearing potential yes / no in order to characterize the patient population and as a basis for contraception requirements, as well as the date of the last menstrual cycle should be documented at each visit.
- The medical examination will include height and body weight, smoking and alcohol history, relevant medical history and concomitant therapy, review of inclusion and exclusion criteria, review of vital signs (BP, PR), 12-lead ECG, laboratory tests including pharmacogenomics sampling, drug screen, and a physical examination including abbreviated neurological exam.

Run-in Period

If intake of any of the restricted medications was identified, investigator will evaluate whether discontinuation of this treatment is justified and would not jeopardize the patient's safety. If discontinuation of restricted medication is possible, the patient will be advised to stop the intake of the prohibited drugs immediately (ad minimum 2 weeks prior to the planned base-line visit).

[figure not shown]
This decision and date of discontinuation must be documented in the patient notes.

Baseline Conditions

Approximately 2 weeks before planned randomisation visit on day 1, patients preliminary confirmed to be eligible for study participation will undergo base-line evaluation Visit 2 (day -14 to -16).

The following will be performed/collected:

- Urine drug screen
- S-UPPS-P
- BIS-11

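### Two eligibility and safety rules contradict themselves: exclusion 14 omits the hypertension history that Section 1.4.2 says is excluded, and Section 4.2.2.1 lists blood-pressure drugs as prohibited yet usable with caution

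*Protocol*

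**What the plan says.** **Hypertension.** Protocol Section 1.4.2 (Risks) says atomoxetine can affect heart rate and blood pressure and gives two mitigations. The first is exclusion of several groups, with references to Section 3.3.3; a history of relevant hypertension is one of those groups. The second is measurement of heart rate and blood pressure before and during treatment. In Section 3.3.3, exclusion 14 covers a relevant history of orthostatic hypotension, fainting or blackouts and does not mention hypertension.

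**Drugs.** Section 4.2.2.1 opens with "Following medications are prohibited during the treatment period". Its first bullet bans psychotropics, CYP2D6 inhibitors and "sympathomimetics, Monoamine Oxidase Inhibitors (MAOI) should not be taken for two weeks before, during and 2 weeks after treatment with Atomoxetine". Its second bullet, under the same lead-in, says "Antihypertensive Drugs, Pressor Agents (e.g., dopamine, dobutamine), beta 2 agonists or other drugs that increase/decrease blood pressure should be used cautiously". Further down come a written exception, "Stable therapy with SSRI might be continued with caution as judged by investigator", and a clause for adverse events, "any treatment deemed necessary per the clinical judgment of investigator for the management of AEs considering patient safety is allowed". The section closes with "Investigators are encouraged to adhere to the restrictions listed in the" Appendix 10.2, or contact with the sponsor.

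Exclusion 16 bars patients who need or wish to stay on restricted medication and points to 4.2.2.1. Inclusion 4 requires willingness to stop relevant co-medication and points to 4.2.2.1 and Appendix 10.2.

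**The concern.** Sites work from the numbered criteria. Section 6.2.2 allows randomisation once they are met, Section 8.3.1 requires source evidence for each of them, and Section 3.3 defines randomisation in error by them. A safeguard that stands only in the risk section is therefore not applied at the gate. A patient with past relevant hypertension can satisfy every numbered criterion although 1.4.2 says that patient is excluded.

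The drug list has a similar effect. Exclusion 16, inclusion 4, the run-in review in 6.2.1 and the treatment-discontinuation rule in 3.3.4.1 all depend, directly or by reference, on which drugs 4.2.2.1 restricts. If one list both bans and permits a class, two investigators can act differently on the same patient and each cite the protocol.

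The setting gives this some weight. The first dose is 80 mg, while Section 4.1.2 describes initiation at 40 mg for at least 7 days (80 / 40 = 2 times), and the drug raises pulse and blood pressure.

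**Working it through.** No statistical calculation applies. The check is to set the current texts side by side. Neither conflict comes from a redaction or from the amendment log.

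**1. Hypertension: which numbered criterion would catch the patient?**

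| Patient | Criterion in 3.3.3 | Result |
|---|---|---|
| Repeated readings outside 90 to 145 / 45 to 90 mmHg | Exclusion 6 | Excluded |
| Clinically relevant blood-pressure finding at examination | Exclusion 5 | Excluded |
| Current cardiovascular disease judged clinically relevant | Exclusion 10 | Excluded |
| Hypertension that counts as a known contraindication to atomoxetine | Exclusion 15 | Excluded; reach depends on the product label, which is not in the documents |
| Controlled hypertension, readings in range, not judged a relevant current disease | None by name | Can be admitted |
| Past hypertension, now resolved | None by name | Can be admitted |

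Section 1.4.2 would exclude the last two rows whenever the history is relevant. Exclusion 14 is where that rule belongs, since it carries the rest of the same phrase almost word for word.

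**2. Beta-2 agonists and dobutamine-type pressors: what do the other texts say?**

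- Bullet 1 of 4.2.2.1 bans sympathomimetics. Section 1.2 places dobutamine and beta-2 agonists among the direct-acting sympathomimetics.
- Appendix 10.2, on drugs that may prolong QT, has a section listing beta-2 agonists by name.
- Inclusion 4 and the last line of 4.2.2.1 both refer to Appendix 10.2.
- Section 1.2 suggests not combining atomoxetine with the drugs in that appendix, and 1.4.2 says users of QT-prolonging drugs are excluded.

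All of these point to prohibition. Bullet 2 alone points to cautious use, so here it contradicts the rest. It also does not read as a deliberate exception: the SSRI paragraph shows how this protocol words one, and these classes have no such text.

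**3. Antihypertensives and other blood-pressure drugs outside Appendix 10.2: what settles the rule?**

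- The lead-in of 4.2.2.1 says prohibited; the bullet says use with caution.
- Section 1.2 notes an interaction with antihypertensives but states no ban.
- Appendix 10.1, titled as the restricted list, covers only CYP2D6 inhibitors and MAOIs.
- Section 6.2.1 says "If intake of any of the restricted medications was identified, investigator will evaluate whether discontinuation of this treatment is justified", and a drug to be discontinued must stop "ad minimum 2 weeks prior to the planned base-line visit". That procedure presupposes a known list of restricted drugs.

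Nothing decides the matter. The two conflicts can meet in one person: a patient with controlled hypertension on a stable antihypertensive is not named in exclusion 14 and has no clear drug rule either.

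**The case against.** The strongest reply is that little is left uncovered. Exclusions 5, 6 and 10 deal with current hypertension, exclusion 15 may add label contraindications, and the word relevant leaves the decision to the investigator whichever text is followed. On drugs, the second half of exclusion 16 bars anything likely to interfere with safe conduct, 6.2.1 requires a documented decision, and sponsor contact is offered. The 80 mg first dose is justified in 4.1.2 and given under surveillance until 4 h after dosing, and SAP 4.11.3 schedules vital signs before and 4 h after that dose.

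Most of this stands, and it keeps the point minor. It does not remove the conflict: discretion and sponsor contact allow a decision case by case, but they do not say which of two opposite statements is the rule. Nor do they put into the criteria an exclusion that the benefit-risk section presents as already there.

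Three stronger readings are tempting, and the documents do not support them:

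- *That a regular beta-2 agonist user has no rule at all.* Inclusion 4 with Appendix 10.2, bullet 1 and 1.4.2 lean clearly to prohibition; the fault is one contrary bullet.
- *That hypertensive patients in general can enter.* Out-of-range readings and clinically relevant current disease are excluded.
- *That the results are affected.* Protocol 7.2.2 handles concomitant therapy by treatment policy, and neither conflict enters the ANCOVA, the endpoints or the sample size.

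**Conclusion.** The point holds as a minor internal inconsistency in eligibility and safety text, in two parts.

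1. Exclusion 14 lacks the history of relevant hypertension that 1.4.2 says is excluded. The gap is mainly past hypertension, or controlled hypertension not judged a relevant current disease.
2. Section 4.2.2.1 puts drugs to be used with caution under a prohibition on which exclusion 16 depends. For beta-2 agonists the bullet contradicts the rest of the protocol. For antihypertensives and other blood-pressure drugs outside Appendix 10.2 the rule is unresolved.

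The documents give no count of patients whose eligibility would change, and none is estimated here. It is probably small, given the age range of 18 to 45 and the other exclusions. Nothing shows that any patient was wrongly admitted or harmed. The conclusion assumes that sites apply the numbered criteria as written, and that the label, which is not available here, does not close the hypertension gap through exclusion 15.

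**What to change.** - **Exclusion 14:** insert hypertension ahead of orthostatic hypotension, so that the criterion matches Section 1.4.2.
- **Section 4.2.2.1:** split the list into prohibited drugs and drugs permitted with caution, with each class in one list only. Put beta-2 agonists and sympathomimetic pressors under prohibited unless an explicit exception is written, in the way it is done for SSRIs. Decide on antihypertensives and the remaining blood-pressure drugs and say so. Keep the clause that allows any treatment needed for an adverse event.
- **Linked text:** align inclusion 4, exclusion 16 and Appendix 10.2 with the two lists. If beta-2 agonists are to be permitted, mark them in Appendix 10.2 as an exception to the QT-drug exclusion in 1.4.2.

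The cost is amendment wording, an update of the eligibility checklist and possibly a few more screen failures. The analysis plan does not change.
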